9.2 Subject Accountability

The number and percent of subjects who were enrolled into the OLE study, received IP, completed IP, discontinued IP and reasons for discontinuing during the OLE study, completed the OLE study, and discontinued the OLE study and reasons for discontinuing will be summarized by the randomized treatment group in parent study and overall.

OLE enrollment by region, country and investigator and, key study dates for the first subject enrolled, last subject enrolled and last subject's end of study will be presented.

9.3 Important Protocol Deviations

Important Protocol Deviations (IPDs) categories are defined by the study team before the first subject's visit and updated during the IPD reviews throughout the study prior to database lock. These definitions of IPD categories, subcategory codes, and descriptions will be used during the course of the study. Eligibility deviations are defined in the protocol.

The number of subjects reporting Protocol Deviations and Important Protocol Deviations due to COVID-19 impact will be summarized in a table. A Protocol Deviation listing of subjects impacted due to COVID-19 impact will also be provided.

9.4 Demographic and Baseline Characteristics

All baseline tables will be summarized by the randomized treatment groups in **parent** study. Baseline tables will summarize the following: baseline characteristics, demographics, cardiovascular medical history, laboratory parameters, physical measurements and lipid regulating medication.

9.5 Efficacy Analyses

Table 9-1. Endpoint Summary Table

Endpoint	Primary Summary (Long-Term Safety Analysis Set and OLE Safety Analysis Set)
Primary Endpoint	
Treatment emergent adverse events 
• Adverse events• Serious adverse events• Fatal adverse events• AEs leading to withdrawal from IP• Device-related adverse events• Disease related events	Subject incidence and exposure adjusted subject incidence rate
Secondary Endpoints	
Percent change of LDL-C from baseline	Summary statistics at each scheduled visit
Achieving an LDL-C level < 40 mg/dL	Summary statistics at each scheduled visit
Exploratory Endpoints	
Change and percent change from baseline 
• non-HDL-C• ApoB• Total cholesterol• Lp(a)• Triglycerides• HDL-C• LDL-C• VLDL-C• ApoA1	Summary statistics at each scheduled visit

Endpoint	Primary Summary (Long-Term Safety Analysis Set and OLE Safety Analysis Set)
Subject incidence of events positively reviewed by the CEC: 
○ All deaths
▪ Cardiovascular death▪ Non-cardiovascular death▪ Undetermined Cause of death○ Cardiovascular events of interest:
▪ Myocardial Infarction (MI)▪ Coronary revascularization▪ Hospitalization for unstable angina▪ Heart failure▪ Cerebrovascular Events▪ Coronary heart disease death	Subject incidence of events positively reviewed by the CEC

9.5.1 Analyses of Primary Endpoint

The current Medical Dictionary for Regulatory Activities version at the time of data lock will be used to code all adverse events (AEs) and disease related events to a system organ class and a preferred term.

Treatment-emergent adverse events are events with an onset after the administration of the first dose of investigational product as defined in [Section 5.3](#).

The subject incidence and exposure-adjusted subject incidence rate of all treatment-emergent adverse events, serious adverse events, fatal adverse events, adverse events leading to withdrawal of evolocumab, device-related adverse events, and disease-related events will be tabulated by system organ class (SOC), high level term (HLT), and preferred term (PT) in alphabetical order for the overall OLE study period using the OLE safety analysis set. These events will also be presented by yearly subject exposure time intervals. All adverse event summaries for the primary analysis of the primary endpoint will include all treatment-emergent events reported on the Event eCRF, including CEC reviewed events and disease related events.

The analyses described above (subject incidence, exposure-adjusted subject incidence rate) will also be performed combining data from the OLE study and the **parent** study

using the **OLE safety analysis set** and also be analyzed separately for the subgroup of subjects who were randomized to and received evolocumab group in the parent study with ≥ 7 years of the combined exposure for evolocumab across the parent and OLE study. Events from **parent** study classified as Target IP TEAEs will be included (adverse events occurring from the first dose of IP date to 30 days after the last dose of IP date or EOS, whichever occurs first). Disease-related events from the OLE study will be reclassified as adverse events and positively reviewed events from the OLE study will not be included to remain consistent with **parent** study adverse event reporting. This analysis will be presented by the **randomized treatment in the parent study**.

Subject incidence of treatment emergent and serious adverse events occurring in at least 1% of the subjects by preferred term will be provided in descending order of frequency for the overall OLE study period only **and combined parent and OLE study periods**.

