4.1 Inclusion Criteria

- 101 Subject has provided informed consent prior to initiation of any study-specific activities/procedures.
- 102 Subject had completed FOURIER (Study 20110118) while still receiving assigned Investigational Product.

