4.2 Exclusion Criteria

- 201 Permanent discontinuation of Investigational Product during FOURIER for any reason including an adverse event or serious adverse event.
- 202 Currently receiving treatment in another investigational device or drug study, or less than 4 weeks since ending treatment on another investigational device or drug study(ies). Other investigational procedures while participating in this study are excluded.
- 203 Subject likely to not be available to complete all protocol-required study visits or procedures, and/or to comply with all required study procedures to the best of the subject and investigator's knowledge.
- 204 History or evidence of any other clinically significant disorder, condition or disease that, in the opinion of the investigator or Amgen physician, if consulted, would pose a risk to subject safety or interfere with the study evaluation, procedures or completion.
- 205 Subject has known sensitivity to any of the active substances or excipients (eg, sodium acetate) to be administered during dosing.
- 206 Females who are pregnant or breastfeeding or planning to become pregnant or breastfeed during treatment with evolocumab and for an additional 15 weeks after treatment with evolocumab discontinues.
- 207 Female subjects of childbearing potential unwilling to use an acceptable method of effective contraception during treatment and for an additional 15 weeks after the last dose of protocol-required therapies. Refer to [Section 6.8](#) for additional contraceptive information.

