4.2 Subgroups

The planned subgroups include the following:

- Baseline age (< 65 years, ≥ 65 years; < 75 years, ≥ 75 years)
- Sex (male, female)
- Race (white, non-white)
- Prior non-hemorrhagic stroke (yes, no)
- Symptomatic PAD (yes, no)
- Prior MI (No, < 1 year, 1 - < 2 years, ≥ 2 years)
- Baseline PCSK9 level (< median, ≥ median)
- Baseline LDL-C by quartiles (Q1, median, Q3)
- Baseline HDL-C by quartiles (Q1, median, Q3)
- Baseline triglycerides by quartiles (Q1, median, Q3)
- Baseline hsCRP (< 2 mg/L, ≥ 2 mg/L)
- Ezetimibe use at baseline (yes, no)
- ACC/AHA high statin background therapy intensity at baseline (yes, no)
- History of type 2 diabetes (yes, no)
- Heterozygous Familial Hypercholesterolemia (HeFH) at OLE enrollment (definite, probable, neither definite nor probable)
- **Subjects who were randomized to and received evolocumab group in the parent (i.e., FOURIER) study with ≥ 7 years of the combined exposure for evolocumab across the parent and OLE studies.**

5. Definitions

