Mortality	Death endpoint date reviewed by CEC in OLE study – randomization date in the parent study +1	For subjects who died not due to death endpoint, the censoring date is the death date (reviewed by CEC) in OLE study For remaining subjects, the censoring date is max (EOS date, last known survival status date from eCRF page(s)) in the OLE study
For analyses based on OLE data only		
Composite or Non-mortality	First event onset date reviewed by CEC in OLE – enrolment date in OLE study +1	EOS date in OLE study
Mortality	Death endpoint date reviewed by CEC in OLE study – enrolment date in OLE study +1	For subjects who died not due to death endpoint, the censoring date is the death date (reviewed by CEC) in OLE study For remaining subjects, the censoring date is max (EOS date, last known survival status date from eCRF page(s)) in the OLE study

Patient-years of follow-up for treatment emergent adverse events

For analyses based on combined both the parent and OLE studies:

- 1) Subjects had first event in parent study: date (first event) – date (first dose date in FOURIER) + 1
- 2) Subjects had first event in OLE: study exposure in parent study + (date (first event) – first dose date in OLE + 1)
- 3) Subjects didn't have events: study exposure in parent study + (min [date (EOS in OLE), date (last dose date in OLE)+30] – first dose date in OLE + 1)

For analyses based on OLE study:

- 1) Subjects had events: date (first event in OLE) – date (first dose date in OLE) + 1

2) Subjects didn't have events: min [date (EOS in OLE), date (last dose date in OLE)+30] – date (first dose date in OLE) + 1

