5.3 Other Study Related Definitions

Treatment-emergent adverse event

Events are categorized as Adverse Events (AEs) or **Disease-related Events (DREs)** starting on or after first dose of investigational product as determined by the flag indicating if the event started prior to the first dose on the Events eCRF and up to the EOS/Safety Follow-up visit or 30 days after the last administration of evolocumab, whichever is earlier.

Treatment-Emergent Disease-Related Events

Events categorized as Disease-related Events (DREs) defined in Protocol Section 9.1.1 starting on or after first dose of investigational product as determined by the flag indicating if the disease-related event started prior to the first dose on the Events eCRF and up to the EOS/Safety Follow-up visit or 30 days after the last administration of evolocumab, whichever is earlier.

Analytical Study Week Assignments

Analytical windows will be used to assign parameters to study weeks. The algorithm is provided in [Appendix A](#).

Investigational Product (IP)

Investigational product includes evolocumab 140 mg every two weeks (Q2W) and 420 mg monthly (QM).

IP Exposure Period in Months (Parent study)

For subjects whose last IP dose is Q2W:

IP exposure period = [min(last IP dose date in parent study + 14 days, EOS date) – first IP dose date in parent study + 1] / 365.25 x 12

For subjects whose last IP dose is QM:

IP exposure period = [min(last IP dose date in parent study + 28 days, EOS date) – first IP dose date in parent study + 1] / 365.25 x 12

IP Exposure Period in Months (For OLE period)

For subjects whose last IP dose is Q2W:

IP exposure period in OLE period = [min(last IP dose date in OLE period + 14 days, EOS date) – first IP dose date in OLE period + 1] / 365.25 x 12

For subjects whose last IP dose is QM:

IP exposure period in OLE period = [min(last IP dose date in OLE period + 28 days, EOS date) – first IP dose date in OLE period + 1] / 365.25 x 12

IP Exposure Period in Months (For the combined parent and OLE periods)

For each subject, IP exposure in combined periods is the sum of the IP exposure in the parent study (defined above) plus the IP exposure in the OLE period (defined above).

Study Exposure Period in Months (Parent study)

For each randomized subject, study exposure period = [(EOS date in parent study – Randomization date) + 1] / 365.25 x 12

Study Exposure Period in Months (For OLE period)

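### The subgroup with at least 7 years of evolocumab exposure is defined by staying on drug, so its rate of AEs leading to withdrawal is low by construction, and any fatal-AE row is conditioned the same way

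*SAP*

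**What the plan says.** SAP 4.2 lists a subgroup of subjects randomized to and treated with evolocumab in the parent study "with ≥ 7 years of the combined exposure for evolocumab across the parent and OLE studies". SAP 9.5.1 then applies the subject incidence and exposure-adjusted rate analyses, on combined parent and OLE data, separately to those "who were randomized to and received evolocumab group in the parent study with ≥ 7 years of the combined exposure for evolocumab". The event categories carried over include fatal AEs and AEs leading to withdrawal of evolocumab.

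SAP 5.3 supplies the exposure definition: "For each subject, IP exposure in combined periods is the sum of the IP exposure in the parent study (defined above") plus that in the OLE. Within each study it runs from first dose to last dose plus 14 days (Q2W) or 28 days (QM), capped at end of study. For a monthly dose in the OLE the end point is "min(last IP dose date in OLE period + 28 days, EOS date"). Interruptions are not subtracted. SAP 5.3 also defines a study exposure, which runs to end of study whether or not drug is taken. SAP 4.2 and 9.5.1 do not say which of the two the 7-year rule uses.

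For the combined rate, SAP 5.1 counts parent time in full. Subjects without an event contribute "study exposure in parent study + (min [date (EOS in OLE), date (last dose date in OLE)+30"] less the first OLE dose date, plus 1 day. For those with a first event in the OLE the rule begins "Subjects had first event in OLE: study exposure in parent study" and adds OLE time up to the event.

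OLE subjects must have "completed FOURIER (Study 20110118) while still receiving assigned Investigational Product" (Protocol 4.1), and Protocol 4.2 excludes "Permanent discontinuation of Investigational Product during FOURIER for any reason including an adverse event or serious adverse event".

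**The concern.** Membership is known only after follow-up, and it depends on the outcome being tabulated. A subject whose AE leads to a permanent stop in, say, cumulative year 5 is removed from the subgroup, and the event goes too. Subjects who remain bring about 7 years of person-time in which neither a permanent stop nor a death was possible.

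The SAP version history says the subgroup was added to look at the effect of long-term exposure, and the primary objective is safety and tolerability. AE-driven withdrawal is a direct measure of tolerability. A rate far below the full-set rate, shown under a 7-year exposure label, invites the reading that long exposure is well tolerated when the selection rule produced the gap. No section adds a landmark, a risk-set restriction or a caution. Other AE categories can accrue throughout the 7 years. They are affected only indirectly, in a direction that cannot be established here.

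**Working it through.** **The plan's own figures.** The SAP states no figure for this subgroup. Its one planning figure, the 95% CI widths in Table 3-1, reproduces in all eight rows as 2 × 1.96 × √(p(1−p)/1600) (for example p = 1% gives 0.975 percentage points), but it does not bear on this point.

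**Inputs from the documents.** The week 260 visit is study day 1821 (SAP Appendix A), so OLE exposure is T = 1821/365.25 = 4.986 years. The threshold is 7 years. The dosing credit c is 14 or 28 days (0 is shown as well). Parent time has no permanent stops or deaths (Protocol 4.1 and 4.2).

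**Assumptions, not in the documents.** Parent exposure p is 2.25 to 3.5 years. The constant OLE hazard h is 0.5 to 4 per 100 person-years (PY), for stops due to the AEs that remain once positively reviewed OLE events are removed.

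**Earliest last dose that still gives membership**, at OLE time 7 − p − c:
- p = 2.25: about week 244 (QM) or 246 (Q2W)
- p = 3: week 205 or 207
- p = 3.5: week 179 or 181

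**Closed form**, with the event placed at the stop. The window in which a member can stop is w = p + T − 7 + c.
- Subgroup rate = (1 − e^(−hw)) / (7 − c + (1 − e^(−hw))/h)
- All evolocumab-randomized OLE subjects = (1 − e^(−hT)) / (p + (1 − e^(−hT))/h)

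*Example:* p = 3, h = 0.02, c = 14 days = 0.038 y. Then w = 1.024 and 1 − e^(−hw) = 0.02027. The subgroup rate is 0.02027/(6.962 + 1.014) = 0.254 per 100 PY. For all subjects, 1 − e^(−hT) = 0.0949 and the rate is 0.0949/(3 + 4.745) = 1.225 per 100 PY. The subgroup is 79% lower.

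| Parent years | Subgroup rate per 100 PY, h = 0.02 (c = 0 to 28 days) | All evolocumab-randomized | Lower by, over h = 0.005–0.04 |
|---|---|---|---|
| 2.25 | 0.065–0.086 | 1.357 | 93.6–95.3% |
| 2.5 | 0.129–0.149 | 1.310 | 88.5–90.2% |
| 3 | 0.245–0.264 | 1.225 | 78.3–80.2% |
| 3.5 | 0.346–0.364 | 1.151 | 68.2–70.1% |

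Subject incidence at h = 0.02 is 0.47–0.62% (p = 2.25) to 2.93–3.08% (p = 3.5), against 9.49%.

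**Simulation under the SAP 5.1 person-time rule** (to AE onset, or to the earlier of end of study and last dose + 30 days; 14-day credit). Other stops were set at 0, 2 or 5 per 100 PY and the mean lag from AE onset to stop at 0 or 3 months. The deficits were 94.1–94.8% (p = 2.25), 78.2–80.1% (p = 3) and 68.2–69.6% (p = 3.5). With p spread evenly over 2.25–3.5 years the deficit was 81.0–82.4%. With the 3-month lag, 69–71%, 28–29% and 19–20% of members' events (p = 2.25, 3, 3.5) began before year 7 and were still counted. It is the last dose, not the AE onset, that cannot come early.

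**Is it earlier randomization instead?** A second simulation used parent time uniform over 2–3 years and hazards of 1 (AE stop), 1.5 (fatal) and 3 (other stop) per 100 PY. Restricting to subjects with enough parent time to reach 7 years left the withdrawal rate at 0.635 against 0.636 per 100 PY. Requiring 7 years of actual exposure cut it to 0.065. The drop comes from conditioning on staying on drug.

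**The case against.** The strongest reply is that the unconditional picture is already planned. SAP 9.5.1 presents the same events by yearly exposure interval for the OLE period, SAP 9.2 tabulates discontinuation and its reasons by parent arm, and every permanent stop in this population falls in the OLE. The analysis is descriptive (SAP 9.1) and the 7-year condition is in the subgroup's name. This all stands, and it is why the primary results are safe. It does not repair the subgroup's own withdrawal row, and the planned intervals run by OLE year rather than by cumulative exposure.

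Three qualifications also stand.
- The SAP does not define an AE leading to withdrawal as a final stop. An AE so coded and followed by resumed dosing could count before year 7.
- The 68–95% range rests on assumed parent durations. The same formulas give about 98–99% at 2.05 years and about 58–60% at 4 years.
- The fatal row may be nearly empty even in the full set. The CEC reviews all deaths (SAP 9.1), and SAP 9.5.1 removes positively reviewed OLE events from the combined analysis. Deaths are covered by the yearly Kaplan–Meier estimates in SAP 9.5.3.

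If study exposure was meant, only the fatal row is affected. The wording points more naturally to IP exposure, but the SAP should say so.

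**Conclusion.** The point holds and should be corrected. Read as combined IP exposure, the 7-year rule makes the subgroup's withdrawal row low by construction: about 68–95% below all evolocumab-randomized OLE subjects for 2.25–3.5 parent years, and almost insensitive to the hazard over 0.5–4 per 100 PY. Parent duration and hazard are assumptions. The direction, for permanent stops, is not. The fatal row is conditioned in the same way, but no size is claimed for it. Neither row can be read as a 7-year rate of AE-driven withdrawal or of fatal AEs. The primary OLE-period analysis and the full-set combined analysis do not use the 7-year condition.

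**What to change.** 1. In SAP 4.2 and 9.5.1, state that combined exposure means the combined IP exposure of SAP 5.3.
2. For AEs leading to withdrawal and fatal AEs only, replace the subgroup rate with a table of all evolocumab-randomized subjects in the OLE safety analysis set, by yearly interval of cumulative evolocumab exposure through and beyond year 7. Give the number at risk, events and person-years per interval. Place events at last dose or death, and note that this differs from the first-event date used in SAP 5.1. Note also that parent-period intervals contain no permanent stops or deaths because of the entry criteria.
3. If the two rows stay in the subgroup table, either count only stops or deaths and person-time after year 7 or omit the rate. Label them as conditional on 7 years alive and on evolocumab.
4. For deaths, refer to the yearly Kaplan–Meier estimates in SAP 9.5.3. Leave the other AE categories as planned, with a footnote on the selection.

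The cost is SAP wording and one extra set of tables for two rows, extending a display already planned for the OLE period. The drawback is thin data beyond year 7. With 800 evolocumab-arm subjects (assumed half of 1600), 2.25–3.5 parent years, 2 AE stops and 0–5 other stops per 100 PY, there would be about 134–1092 PY and 3–22 AE-driven stops.

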9.5.2 Analyses of Secondary Endpoints

Summary statistics of the secondary endpoints (percent change of LDL-C from baseline and achieving an LDL-C level < 40 mg/dL) will be analyzed based on the OLE Safety Analysis Set at each scheduled visit **for the overall parent and OLE study periods**.

9.5.3 Analyses of Exploratory Endpoints

The change and percent change from baseline in lipid parameters at each scheduled visit will be summarized based on the OLE Safety Analysis Set **for the overall parent and OLE study periods**. For continuous exploratory endpoints, summary statistics (number of subjects, mean, median, standard deviation or standard error, first and third quartiles, minimum, and maximum) at all scheduled visits will be calculated. Subject incidence, **exposure-adjusted subject incidence rate, and yearly Kaplan Meier (K-M) estimates of** positively reviewed events (by an independent external CEC) will be summarized **for both the OLE study period and combined parent and OLE study periods**. **All deaths will be summarized by cardiovascular death (including coronary heart disease death), non-cardiovascular death and undetermined cause of death. A sensitivity analysis will be performed for the following composite endpoints:**

- time to cardiovascular death, myocardial infarction, hospitalization for unstable angina, stroke, or coronary revascularization, whichever occurs first
- time to cardiovascular death, myocardial infarction, or stroke, whichever occurs first

In this analysis, cardiovascular events which occurred during the gap between subjects End of Study date in the parent study and OLE study enrolment date will be included in the time to event analysis.

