8.3.2 Reasons for Removal From Study

Reasons for removal of a subject from the study are:

- decision by sponsor
- withdrawal of consent from study
- death
- lost to follow-up

Approved

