5.1 Study Time Points

Baseline

The baseline value is defined as the subject's baseline value from the parent study (FOURIER), unless otherwise specified.

First Dose Date of Investigational Product (IP)

For each subject, the first dose date of IP is the date of the first administration of evolocumab in **this OLE study**.

End of Investigational Product (EOIP) Date

For each subject, end of investigational product is the date reported on End of Investigational Product Administration eCRF.

Last Dose Date of Investigational Product

For each subject, the last dose date of investigational product is defined as the date of the last administration of investigational product (evolocumab or placebo).

If the last dose was administered in-clinic, then the Last IP Dose Date is the last start date captured on the IP Administration (In-Clinic) eCRF page.

If the last dose was administered at a non-investigator site location, then the Last IP Dose Date is defined as the final dose date reported by the subject on the Non-Clinic Final Investigational Product Dose Date eCRF page.

End of Study (EOS) Date

For each subject, the end of study date is defined as the last day that protocol-specified procedures are conducted for an individual subject, including safety follow-up and survival assessment. The EOS date is recorded on the End of Study eCRF.

Enrollment Date

The enrollment date for each subject is recorded on the Subject Enrollment eCRF **in the OLE study**.

Study Day 1

Study day 1 is defined as the day of the first administration of evolocumab in the study or the day of enrollment for subjects who are not administered any dose of evolocumab.

Study Day

For each subject, and for a given date of interest, study day is defined as the number of days since study day 1:

Study day = (date of interest – study day 1 date) + 1

If the date of interest is prior to the study day 1:

Study day = (date of interest – study day 1 date)

Study End Date

The study end date is the last EOS date of all enrolled subjects.

Categories of Time-to-first-event Endpoints

All time-to-first-event endpoints in this study are categorized below.

- **Composite**
 - **time to cardiovascular death, myocardial infarction, hospitalization for unstable angina, stroke, or coronary revascularization, whichever occurs first**
 - **time to cardiovascular death, myocardial infarction, or stroke, whichever occurs first**

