 - **time to cardiovascular death or hospitalization for worsening heart failure, whichever occurs first**
 - **time to ischemic fatal or non-fatal stroke or transient ischemic attack, whichever occurs first**
 - **time to the first fatal and non-fatal myocardial infarction**
 - **time to the first fatal and non-fatal stroke**
- **Non-mortality**
 - **time to the first coronary revascularization**
- **Mortality**
 - **time to cardiovascular death**
 - **time to coronary death**
 - **time to death by any cause**

Censoring date

Endpoints are censored differently according to the endpoint categories. The censoring schema are described in below:

- censoring date for the composite and non-mortality endpoints is the EOS date in the OLE study.
- censoring (or time-to-event) for mortality endpoints are detained in appendix C.

Time-to-first-event Definition

- For the time-to-first-event analysis based on combined the parent and OLE data, the events adjudicated as positive in the parent study and occurred prior to or on subject last confirmed survival status date in the parent study (i.e., primary analysis in the parent study; please see the definition in the parent study SAP version 3.1 dated Aug 09, 2016) are included in addition to the events reviewed as positive in the OLE study (defined as below).

For the time-to-first-event analysis based on the OLE data only, mortality events reviewed as positive and occurred prior to or on later of (the EOS date or last known survival status date from eCRF page(s) in this OLE study) and non-mortality events reviewed as positive and occurred prior to or on the EOS date are included. For those subjects who already experience such event in the parent study, their time to event and censor flag are same as those in the parent study.

- For those subjects who didn't experience such event in the parent study, the derivation of the time-to-event and censoring date is presented below

For analyses combined both the parent and OLE studies		
Endpoint	Time-to-event for subjects with events	Censoring date for subjects without events
Composite or Non-mortality	First event onset date reviewed by CEC in OLE study – randomization date in the parent study +1	EOS date in OLE study

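### The yearly Kaplan-Meier risks of CEC events censor deaths outside the endpoint and so modestly overstate cumulative incidence; Aalen-Johansen estimates should stand beside them

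*SAP*

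**What the plan says.** SAP 9.5.3 summarises CEC-positive events by crude subject incidence, "exposure-adjusted subject incidence rate, and yearly Kaplan Meier (K-M) estimates of" those events, "for both the OLE study period and combined parent and OLE study periods". SAP 5.1 lists the time-to-first-event endpoints: several composites (fatal or non-fatal MI and fatal or non-fatal stroke are listed among them), one non-mortality endpoint, "time to the first coronary revascularization", and three mortality endpoints: cardiovascular death, coronary death and "time to death by any cause".

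Censoring differs by type of endpoint:

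- **Mortality.** The table in SAP 5.1 is explicit: "For subjects who died not due to death endpoint, the censoring date is the death date (reviewed by CEC) in OLE study".
- **Composite and non-mortality.** The only rule is that the "censoring date for the composite and non-mortality endpoints is the EOS date in the OLE study". Nothing separate is said about subjects who die.

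SAP 5.1 defines a subject's EOS date as the "last day that protocol-specified procedures are conducted for an individual subject, including safety follow-up and survival assessment". It does not equate this with the death date. Protocol 8.3.2 opens its list with "Reasons for removal of a subject from the study are", and death is on that list, so a death outside the endpoint leads to an EOS date and hence to censoring.

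Neither document mentions competing risks or cumulative incidence functions. SAP Appendix C, to which 5.1 refers for mortality censoring, shows only its title in the available text, and I draw no conclusion from that.

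**The concern.** K-M treats a censored subject as still able to have the event later. A subject who has died of another cause cannot. If such deaths are censored, one minus K-M estimates the risk that would apply if nobody died of other causes, which is not the share of subjects who actually have the event. The exploratory objective is to describe that incidence. The analysis is descriptive, with no test, so a yearly K-M risk will be read as the absolute risk by that year. The error has one direction within the analysed set and does not shrink with sample size. All-cause death is unaffected, because nothing competes with it.

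**Working it through.** **1. The plan's own figure.** Protocol Table 5 and SAP Table 3-1 give 95% CI widths at N = 1600. The formula 2 × 1.96 × √(p(1−p)/1600) gives 0.975 points at p = 1% and 2.136 at p = 5%. All eight entries reproduce to three decimals. The table is not in dispute and serves here only as a yardstick.

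**2. Inputs.**

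- From the documents: 260 weeks of OLE, about 5 years (Protocol 3.5.1); N = 1600 (Protocol 10.2); completion of the parent study as an entry condition (Protocol 4.1, criterion 102).
- Assumed, because the documents give no rates: constant hazards, event rate h of 1-2% per year, competing death d of 1-3% per year, and a wider grid of h = 0.5-3% and d = 0.5-4%.
- Assumed parent follow-up: 2 years, from the subgroup with at least 7 years of combined exposure in SAP 4.2 (7 − 5).

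**3. OLE, 5 years.**

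- 1 − K-M = 1 − exp(−5h)
- Cumulative incidence = h/(h+d) × (1 − exp(−5(h+d)))

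For h = 0.015 and d = 0.02, 1 − K-M is 1 − exp(−0.075) = 7.23%. The cumulative incidence is 0.4286 × (1 − exp(−0.175)) = 6.88%.

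| h, d (%/year) | 1 − K-M (%) | Cumulative incidence (%) | Excess (points) | Relative | 95% CI width (points) |
|---|---|---|---|---|---|
| 1, 1 | 4.88 | 4.76 | 0.12 | 2.5% | 2.09 |
| 1.5, 2 | 7.23 | 6.88 | 0.35 | 5.0% | 2.48 |
| 2, 2 | 9.52 | 9.06 | 0.45 | 5.0% | 2.81 |
| 2, 3 | 9.52 | 8.85 | 0.67 | 7.6% | 2.78 |

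Differences are taken before rounding. CI widths use the formula in step 1 at the cumulative incidence. Over the wider grid the excess runs from 0.03 to 1.27 points (1.2% to 10.3% relative).

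A simulation at h = 1.5% and d = 2% (1600 subjects, 1000 runs, 2% per year dropout) gave 7.23% for K-M and 6.89% for Aalen-Johansen.

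**4. Combined period, 7 years, events that can occur in the parent years.** Nobody in the analysed set died in the parent study, so d acts only in the last 5 years:

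- Cumulative incidence = 1 − exp(−2h) + exp(−2h) × h/(h+d) × (1 − exp(−5(h+d)))

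For h = 0.015 and d = 0.02 this is 2.96% + 0.9704 × 6.88% = 9.63%. One minus K-M is 1 − exp(−0.105) = 9.97%. The excess is 0.34 points, or 3.5%, against 5.0% in the OLE alone. Over the wider grid it is 0.8% to 7.1%.

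**5. Combined period, cause-specific death.** No death of any cause can occur in the parent years. With 1% per year for the cause and 1% for other causes, 7-year 1 − K-M is 1 − exp(−0.05) = 4.88%, against 4.76% within the set. The relative excess is the same 2.5% as in the OLE alone. If deaths were possible in all 7 years, the cumulative incidence would be 0.5 × (1 − exp(−0.14)) = 6.53%. The combined curve, counted from randomization under SAP 5.1, therefore lies below the risk a randomized patient would face.

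**The case against.** The strongest reply is that K-M is not the main summary. SAP Table 9-1 names subject incidence for CEC events. Crude incidence keeps subjects who die in the denominator, and the exposure-adjusted rate needs no competing-risk correction. The endpoint is exploratory, no inference is planned, and the excess is smaller than the CI width. The SAP's change summary also says that the censoring and time-to-event definitions were added so that OLE and parent results could be compared, which is a reason to keep K-M.

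Most of this stands, and it limits the weight of the point. It does not remove it. K-M is the only planned output that gives risk by year while allowing for incomplete follow-up. Crude incidence falls short when subjects drop out: at h = 1.5%, d = 2% and 2% dropout per year it is 0.015/0.055 × (1 − exp(−0.275)) = 6.56%, against 6.88%. CI width measures random error, whereas this excess is systematic.

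For composite and non-mortality endpoints, censoring at death is an inference. If EOS is recorded well after death, dead subjects stay in the risk set and the excess shrinks. The SAP should settle this.

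A reader might go further in four ways that the documents do not support:

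- **The excess keeps growing over the whole combined period.** With competing death in all 7 years, the 1.5%/2% case would show 7.0% instead of 3.5%. The entry condition rules out deaths in the parent years.
- **Combined-period mortality is overstated from randomization.** Step 5 shows the survival condition working the other way, and more strongly in that example.
- **Older subgroups are hit hardest.** SAP 4.2 lists age groups, but 9.5.3 does not say that K-M is produced by age, and no death rates are given.
- **Cause-specific curves will visibly fail to add up to all-cause death.** Non-cardiovascular death is not among the time-to-event endpoints in SAP 5.1, and coronary death is part of cardiovascular death.

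**Conclusion.** The concern holds in a limited form. Within the OLE safety analysis set, one minus K-M modestly overstates cumulative incidence for every CEC time-to-event endpoint except all-cause death. For composites and for fatal or non-fatal MI or stroke, only deaths outside the endpoint compete, so their competing rate is lower than total mortality.

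At 5 OLE years the excess is about 0.1 to 0.7 percentage points for event rates of 1-2% and competing death of 1-3% per year. In the combined period it is about 1% to 7% relative at 7 years over the wider grid, for events that can occur in the parent years. These sizes rest on assumed constant hazards, an assumed 2 parent years, and censoring at or near death. The direction does not depend on the particular rates. This is a cheap improvement to an exploratory summary; the primary endpoint and the crude CEC incidences are untouched.

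**What to change.** - **SAP 9.5.3:** add yearly Aalen-Johansen cumulative incidence beside K-M for every CEC time-to-event endpoint except all-cause death. Treat death outside the endpoint as the competing event, dated at the CEC death date. Keep K-M for comparison with the parent study.
- **SAP 5.1:** state that, for composite and non-mortality endpoints too, a subject who dies leaves the risk set at the death date.
- **Combined-period outputs:** label mortality curves as conditional on completing the parent study.

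No new data are needed, since SAP 5.1 already uses CEC-reviewed death dates. The cost is a few lines of text, a standard procedure and one extra set of estimates in the report.
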